8.4 OBSERVATION PERIOD FOR ADVERSE EVENT REPORTING

The observation period for AE and SAE reporting in an individual subject will start at the time

ZX008 (Fenfluramine Hydrochloride)
ZX008-1601 Clinical Study PA 4.0 (Japan) 25 July 2022

of giving written informed consent for participation in the current study and finish 15 days after the last dose of study drug or the last visit, whichever is later. For subjects who enroll in the open-label extension (Part 2), ongoing AEs will be followed in that study.

If the investigator becomes aware of an SAE that has started after the observation period has finished, and the event could in some way be associated with IMP (irrespective of whether or not it is considered by the investigator to be causally related to IMP), then this must also be reported to the sponsor (see [Section 8.6](#)).

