- c: The safety follow-up visit will be conducted for subjects who either terminate early from Part 1, or who complete Part 1 but do not enter Part 2. Standard follow-up visits should occur 3 and 6 months after the last dose. If there are any findings at the last post-dose follow-up, a follow-up visit will be repeated every 3 months until resolved or stabilized.
- d: The Visit 8 ECHO must be performed any time between Study Day 40 and Study Day 54. The Visit 12 ECHO must be performed any time between Study Day 90 and Study Day 113; if a subject discontinues early from the study, the ECHO should be scheduled as soon as practical. If the Study Day 43 ECHO was completed ≤ 30 days prior to early termination, the Visit 12 ECHO will not be performed provided the parent/guardian agrees to bring the subject to the clinic for the cardiac follow-up visit.
- e: Females of child-bearing potential
- f: Plasma sample for pharmacokinetic assessment will be conducted prior to the dose at Visit 8 and 1, 2, and 4-6 hours after dose administration.
- g: Plasma sample for assessment of background AED(s) will be conducted prior to the dose of AED(s) at Visits 3, 8 and 12 (Visits 6 and 10 only if clinically indicated). Plasma sample may be collected after the morning dose of AED(s) are taken, if preferable, as long as the time of last dose is accurately recorded.
- h: Study drug/diary dispensed for the Transition Period for subjects entering the open-label extension and for the Taper Period for subjects exiting the study.
- i: Site personnel will review study medication dosing procedure (titration) with parent/caregiver.
- j: Study drug administration begins in the clinic on Study Day 1. Study Day 1 is considered the first day of dosing, even though subjects received an in-clinic dose on Study Day -1. The first dose taken in the clinic will be recorded in the eCRF, but not the subject diary; the next dose on the morning of Study Day 1 will be the first entry in the subject's diary.
- k: Only adverse events related to cardiac safety will be collected at this visit.
- l: Visit 13 may be conducted as a phone call, provided diaries and study medication are returned by this time.
- m: An abbreviated physical and/or neurological examination will be conducted as appropriate based on last exam and reported AEs.
- n: Randomization should not occur prior to receiving approval from the Epilepsy Study Consortium and ERT ECHO results.

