5.5.4 Part 1: Taper Period (for subjects not entering Part 2)

Subjects who complete the Maintenance Period and will not be continuing into Part 2, the open-label extension, and subjects who discontinue from Part 1 early, will be tapered off of study medication. Study medication will be administered as equal doses BID in the morning and in the evening approximately 12 hours apart. Each dose should be separated by a minimum of 8 hours and a maximum of 12 hours. A missed dose of study medication may be taken later up to 8 hours before the next scheduled dose; otherwise, the missed dose should not be given. IMP should be administered using the oral dosing syringe provided.

If the parent/caregiver is unable to administer the full dose due to spillage (eg, dose was spilled during measuring, subject spit dose out during administration), he/she should attempt to give the full dose noting the extra amount used to fulfill the dose. If the subject vomits within the first 15 minutes of administration the dose may be readministered. **Care must be taken not to overdose.** If the amount spilled is not known, the parent/caregiver should not give additional medication to avoid potential overdose.

In order to maintain the blind across all dose groups, all subjects who do not continue into Part 2 will participate in a blinded dose-tapering procedure over the course of 8 days. On the first day of the tapering period subjects in the ZX008 0.8 mg/kg/day group (or 0.5 mg/kg/day for subjects taking concomitant STP) will decrease to a dose of ZX008 0.4 mg/kg/day BID (maximum 30 mg/day or 20 mg/day for subjects taking concomitant STP). After 4 days at this dose level (Study Day 5), subjects in this group will decrease their dose to 0.2 mg/kg/day. Subjects in the ZX008 0.2 mg/kg/day group will decrease their dose to placebo on the first day of tapering while doses in the placebo group will remain constant throughout the tapering procedure. On Study Day 9, all subjects will stop taking study medication. The taper is expected to take a total of 8 days (Table 6). A new bottle of IMP will be started by the subject at each level of the taper step.

ZX008 (Fenfluramine Hydrochloride)
ZX008-1601 Clinical Study PA 4.0 (Japan) 25 July 2022

Table 6: Taper Algorithm for Part 1

| Randomized Group | Taper Step 1 Day 1-4 after study completion or early termination | Taper Step 2 Days 5-8 after study completion or early termination |
|---|--|---|
| ZX008 0.2 mg/kg/day | Placebo | Placebo |

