6. VISIT SCHEDULE

6.1 Part 1

Study procedures for the Part 1 Double-blind Treatment Period will be conducted according to the Schedule of Assessments in Table 1. Time windows for all assessments in Part 1 are detailed in Table 9

Table 9: Time Windows for Assessments in Part 1

| Visit / Procedure | Time window (relative to scheduled visit / procedure) |
|---|---|
| Visit 1 (Clinic; Study Day -29 to -28 or -28 to -27): | Not applicable |
| Visit 2 (Phone; Study Day -15) | ± 3 days |
| Visit 3 (Clinic; Study Day -1; Randomization) | + 4 days ^a |
| Visits 4, 5 (Phone; Study Days 4, 8) | ± 3 days |
| Visit 6 (Clinic; Study Day 15) | ± 4 days |
| Visit 7 (Phone; Study Day 29) | ± 4 days |
| Visit 8 (Clinic; Study Day 43) | ± 4 days |
| Visit 9 (Phone; Study Day 57) | ± 4 days |
| Visit 10 (Clinic; Study Day 71) | ± 4 days |
| Visit 11 (Phone; Study Day 85) | ± 4 days |
| Visit 12 (Clinic; Study Day 99) | ± 4 days |
| Visit 13 (Clinic; Study Day 113; post dosing) | ± 4 days |
| Visit 14 (ECHO clinic; 3-6 months after last dose) | + 30 days |
| Blood collection for ZX008 PK | ± 15 minutes |

AED=antiepileptic drug (s); ECHO=echocardiogram; PK = pharmacokinetics

a In cases where the screening period is extended beyond 28 days, the immediate 28 days before the Randomization visit will be used to calculate the baseline seizure frequency

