6.1.3 POST-DOSE VISIT (CLINIC VISIT 13; STUDY DAY 113)

For subjects entering the Part 2 OLE Treatment Period, the subject will visit the clinic on Day 113, which will also be Part 2 Day 1. The procedures described in [Section 6.2](#) will be followed.

If the subject does not enter the Part 2 OLE Treatment Period (or discontinues from the study early), the subject will visit the clinic on Study Day 113 (or 14 days after the day of discontinuation). If necessary, Visit 13 may be conducted as a phone call, provided diaries and study medication are returned by this time. The following will be recorded/performed:

- Review current seizure activity (number/type/duration) from diary since previous visit
- AEs
- AESIs
- Concomitant medications
- Collect and review diary with parent/caregiver
- Collect used, partially used and unused study medication; perform drug accountability and review with parent/caregiver

6.1.4 CARDIAC FOLLOW-UP VISIT (CLINIC VISIT 14; 3 and 6 months after last dose)

If the subject completes the study but does not enter the Part 2 OLE Treatment Period or discontinues from the study early, the subject will return to the clinic after study drug discontinuation for follow-up cardiac testing. The timing and frequency of exams are in Table 10. Subjects on blinded medication who are found to have been on placebo are not required to participate in follow-up testing once the blind is broken. As the ECHO and ECG will be administered in a separate clinic than the pediatric neurology clinic, an asymptomatic subject receiving a follow-up ECHO and ECG does not require a physical examination.

Subjects with positive findings on safety evaluations at post-dose follow-ups should have

ZX008 (Fenfluramine Hydrochloride)
ZX008-1601 Clinical Study PA 4.0 (Japan) 25 July 2022

repeat examinations every 3 months until the finding is resolved or stable and unlikely to change, with reports submitted as AEs to the ZX008 safety database.

Table 10: Schedule of Post-Treatment Cardiac Follow-up for Part 1

| Parameter | Duration of Blinded ^a or Fenfluramine Treatment | | | Have had any cardiac sign or symptom regardless of the time on study drug ^b |
|--|--|------------------------------|------------------------------------|---|
| | Less than 2 weeks Cumulative | 2 and <13 weeks | >13 weeks | |

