6.2.7 POST-DOSE VISIT (CLINIC Visit 43; 14 DAYS AFTER LAST DOSE OF IMP)

If the subject completes the study (or discontinues from the study early), and is not switching to commercially available drug, the subject will visit the clinic for Visit 43 (14 days after the EOS or day of discontinuation). Visit 43 may be conducted as a phone call if physical and neurological examinations are not clinically indicated, provided diaries (if applicable) and study medication are returned by this time. The following procedures will be performed:

- Review current seizure activity (number/type/duration) from diary since previous visit
- Record AEs
- Perform an abbreviated physical and/or neurological examination as appropriate based on last exam and reported AEs
- Obtain weight
- Record AESI
- Record concomitant medications
- Collect and review diary with parent/caregiver
- Collect used, partially used and unused study medication; perform drug accountability and review with parent/caregiver

6.2.8 CARDIAC FOLLOW-UP VISIT (CLINIC VISIT 44, 45; 3 AND 6 MONTHS AFTER LAST DOSE OF IMP)

If the subject completes Part 2 or discontinues from the Part 2 early, and is not switching to commercially available drug, the subject will return to the clinic for follow-up cardiac testing. The timing and frequency of exams are in Table 12. As the ECHO and ECG will be administered

ZX008 (Fenfluramine Hydrochloride)
ZX008-1601 Clinical Study PA 4.0 (Japan) 25 July 2022

in a separate clinic than the pediatric neurology clinic, an asymptomatic subject receiving a second follow-up ECHO and ECG does not require a physical examination.

Subjects with positive findings on safety follow-up examinations should continue to be followed until the finding is resolved or stable and unlikely to change.

If the subject completes the study (or discontinues from the study early) and is switching to commercially available drug, the subject will complete the EOS visit and follow the drug administration process outlined for commercial product as advised by the subject's physician. The EOS/ET and cardiac follow-up visits are not required.

Table 12. Schedule of Post-Treatment Cardiac Follow-up for Part 2

| Parameter | Duration of Fenfluramine Treatment | | | Have had any cardiac sign or symptom regardless of the time on study drug ^a |
|----------------------|------------------------------------|------------------------------|------------------------------------|--|

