7.2.2 Adverse Events

Adverse events (AEs) will be collected from the time of signing the informed consent form/assent form until the end of the study, including the follow-up clinic visit. Details of the definitions and categorization of AEs, and procedures for the reporting of AEs, are available in [Section 9](#).

Severity and causality of AEs will be evaluated according to the criteria specified in [Section 8.2](#) and [Section 8.3](#), respectively. The observation period for AE reporting is specified in [Section 8.4](#). At the beginning of each visit at the study site, the study personnel will specifically inquire about any AEs that might have occurred since the last study site visit. As described below, an abbreviated physical and/or neurological examination for each subject will be conducted based on reported AEs. All AEs will be recorded on the appropriate eCRF page.

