10.1.5 TREATMENT PERIODS

Baseline Period

The Baseline Period covers the 28 days immediately prior to randomization. The baseline frequency of seizures that lead to drops will be calculated from data collected during this period.

Titration Period

The Titration Period covers the first 14 days of treatment while subjects are titrated to their randomized dose. It begins on the first full day of treatment (Study Day 1) and extends through Study Day 15 regardless of the exact day on which a subject reaches his or her assigned dose. The Titration Period applies to all subjects including placebo recipients.

Maintenance Period

The Maintenance Period covers the 12 weeks following the end of the titration period. It begins on Study Day 16 and extends through Study Day 99.

Titration +Maintenance (T+M) Period

The T+M period combines the Titration and Maintenance periods, beginning on Study Day 1 and extending through Study Day 99. The T+M period is considered the treatment period.

Taper/Transition Period

The Taper/Transition Period begins immediately at the end of T+M period and extends to Visit

ZX008 (Fenfluramine Hydrochloride)
ZX008-1601 Clinical Study PA 4.0 (Japan) 25 July 2022

13, 2 weeks later; ie, from Study Day 99 through Study Day 113.

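### The post-dose visit is timed from end of study rather than from the last taper dose, so up to 8 to 9 of the protocol's own 15 post-dose days lack a clearly scheduled general adverse event enquiry

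*Protocol*

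**What the plan says.** - **Observation period.** Section 8.4 lets AE and SAE observation "finish 15 days after the last dose of study drug or the last visit, whichever is later".
- **Part 1 post-dose visit.** For subjects who do not enter Part 2, Section 6.1.3 states that "the subject will visit the clinic on Study Day 113 (or 14 days after the day of discontinuation"). General AEs are on its list of items. Table 9 allows ±4 days.
- **Taper.** Section 5.5.4 and Table 6 put all such subjects on blinded study medication for 8 further days. The 0.8 mg/kg/day group steps down on active drug through day 8. For the low dose, "Subjects in the ZX008 0.2 mg/kg/day group will decrease their dose to placebo on the first day of tapering". The placebo group stays on placebo.
- **Part 2 post-dose visit.** The heading of Section 6.2.7 places it 14 days after the last dose of IMP. The text beneath it describes "Visit 43 (14 days after the EOS or day of discontinuation"), and Table 2 agrees with the text (Day 2160 for end of study, Day 2174 for Visit 43). The taper in Table 8 lasts 0, 4 or 8 days according to dose.
- **Cardiac follow-up.** Table 1 note k and Table 2 note l both state: "Only adverse events related to cardiac safety will be collected at this visit".
- **Text pointing the other way.** Section 7.2.2 collects AEs "until the end of the study, including the follow-up clinic visit" and has staff ask about AEs at the start of each study-site visit. Section 8.5.1 requires an AE check at each clinical evaluation.

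**The concern.** The observation window is counted from the last dose, but the visit meant to close it is counted from the end of the treatment period. The taper lies between the two, so the visit comes too early for the window. If the table notes govern the cardiac visits, no scheduled contact asks about general AEs in the rest of the window.

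At stake is the ascertainment of non-serious events after stopping, including seizure worsening, which Section 8.1.1 counts as an AE. In Part 1 the seizure diary is collected at Visit 13 and not dispensed again, so the daily record ends there too. Long-term safety is the primary objective of Part 2. Sites also cannot tell when the window closes, because the last visit could mean the post-dose visit or the cardiac follow-up.

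**Working it through.** **Inputs.** Treatment period "beginning on Study Day 1 and extending through Study Day 99" (Section 10.1.5). Taper 4 + 4 = 8 days (Table 6). Visit 13 on Day 113 ±4 (Table 9). Visit 14 on Day 197 (Table 1). End of study Day 2160, Visit 43 Day 2174 (Table 2). Taper by dose (Table 8).

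**The plan's own dates reproduce.** 99 + 14 = 113 and 2160 + 14 = 2174. Both visits are therefore anchored to end of study, not to the last dose.

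**Part 1, subjects not entering Part 2.**
- Last IMP dose: 99 + 8 = Day 107 (Day 106 if taper day 1 is Day 99 itself).
- Visit 13 minus last dose: 113 − 107 = 6 days (7 on the alternative count).
- With the Visit 13 window: 109 − 107 = 2 to 117 − 107 = 10 days.
- Earliest close of the Section 8.4 window: 107 + 15 = Day 122 (Day 121).
- Days after Visit 13 still inside the window: 122 − 113 = 9 (8 on the alternative count). With the visit window, 122 − 117 = 5 to 122 − 109 = 13.
- If the last visit means Visit 14, the stretch after Visit 13 is 197 − 113 = 84 days.

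**Part 2.** Taper counted from the day after end of study:

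| Dose at end (mg/kg/day) | Taper days | Last dose (Day) | Visit 43 minus last dose | Of 15 days, after Visit 43 |
|---|---|---|---|---|
| 0.2 | 0 | 2160 | 14 | 1 |
| 0.4 | 4 | 2164 | 10 | 5 |
| 0.5, 0.6, 0.8 | 8 | 2168 | 6 | 9 |

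The heading of Section 6.2.7 is therefore true only where there is no taper.

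**By arm in Part 1.** All three groups take blinded medication to taper day 8, so counted from the last IMP dose the figure is 6 days in each. Counted from the last active dose, it is 113 − 107 = 6 days at 0.8 mg/kg/day and about 113 − 99 = 14 days at 0.2. Moving the visit to Day 122 would give 122 − 107 = 15 and 122 − 99 = 23, so the difference stays at 8 days. It is a product of the taper scheme, not of the visit date.

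**Reach into the analysis.** Section 10.1.6.2 specifies the by-arm safety summaries for the titration plus maintenance period, which ends on Day 99. Events after Day 107 lie outside them.

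**The case against.** A reader might infer that withdrawal events are missed, and unequally by arm. The documents do not support that.

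- **Missed.** Section 8.4 keeps the period open, so an event after Visit 13 is reportable. Ongoing AEs are followed to resolution or stabilization, and SAEs that begin after the window can still be reportable. What is lacking is scheduled asking.
- **Unequally by arm.** Section 8.4 counts from the last dose of study drug, and on that count the arms are equal. The difference appears only from the last active dose, and the planned by-arm summaries do not cover this period.
- **No general question is ever asked again.** Sections 7.2.2 and 8.5.1 can be read as requiring one at cardiac follow-up, and the document does not say whether they or the table notes prevail. Note k marks the row for AEs of special interest, and how far the general AE row extends cannot be read in the text available.
- **The critical period is covered.** Visit 13 comes 14 days after dose reduction begins and about 6 days after the last dose, with the diary kept through the taper. Nothing in the protocol shows that withdrawal effects cluster in the later days.
- **Scope.** Part 1 leavers are only those not entering Part 2, subjects moving to commercial drug have neither taper nor Visit 43, and Amendment 4.0 addresses remaining subjects in Japan.

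All of this limits the point, but the gap remains. Sections 7.2.2 and 8.5.1 do not clearly close it. Section 6.1.4 lists no general AE enquiry and places the ECHO and ECG in a separate clinic. By Table 10, subjects treated for less than 2 weeks without a cardiac sign or symptom have no cardiac follow-up at all.

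**Conclusion.** The point holds as a mismatch between the observation window and the visit schedule, together with contradictory text on what is asked at cardiac follow-up. Followed as written, the schedule has no clearly scheduled general AE enquiry in the last 8 to 9 of the 15 post-dose days for Part 1 leavers. In Part 2 the same applies at 0.5, 0.6 and 0.8 mg/kg/day, with about 5 days uncovered at 0.4 and 1 at 0.2. The likely consequence is under-solicitation of non-serious AEs. No loss of reportable events and no bias in the Part 1 by-arm summaries is shown.

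This assumes that the full taper is taken and that visits fall on their nominal days. Section 4.5 also allows immediate stopping, in which case the interval is about 14 days. It further assumes that notes k and l govern the cardiac visits; if Sections 7.2.2 and 8.5.1 govern instead, general AEs are asked about, but only months later. The correction is worth making because it is cheap and bears on safety ascertainment.

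**What to change.** 1. Time Visits 13 and 43 from the last dose of IMP, so that a general AE enquiry falls at or after the end of the 15-day window. In Part 1 that means Day 122 or later, with a window that runs only forward, for example +4 days. In Part 2 it means 15 to 19 days after the last dose. Visit 13 may already be a phone call, and so may Visit 43 when examinations are not clinically indicated.
2. Make the heading and text of Section 6.2.7 and the day in Table 2 use the same anchor.
3. Reconcile Sections 7.2.2, 8.4 and 8.5.1 with Table 1 note k and Table 2 note l. State what the last visit means and which AEs are asked about at cardiac follow-up. Reconciling the text alone would move no visit, but would leave the first clear enquiry after the window to a visit months later.

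The cost is protocol wording and one existing contact moved by about 9 days, so subjects who leave stay in contact that much longer. Since Amendment 4.0 concerns remaining subjects in Japan, the Part 2 correction is probably the one that can still take effect. No change to dose or taper is implied.

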8.5 ADVERSE EVENT REPORTING

8.5.1 Adverse Events

At each clinical evaluation, the investigator (or delegate) will determine whether any AEs have occurred. Adverse events will be recorded in the AE page of the eCRF. If known, the medical diagnosis of an AE should be recorded in preference to the listing of individual signs and symptoms. The investigator must follow up on the course of an AE until resolution or stabilization. If an AE is ongoing after the end of study visit, the AE will continue to be followed up until resolution or stabilization.

If, during the study period, a subject presents with a pre-existing condition that was not noted at the time of study entry, the condition should be retrospectively recorded in the Medical History section of the eCRF.

8.6 SERIOUS ADVERSE EVENTS REPORTING

This study will comply with all applicable regulatory requirements and adhere to the full requirements of ICH Topic E2A ([Clinical Safety Data Management: Definitions and Standards for Expedited Reporting \[1994\]](#)).

In the event of a SAE the investigator or delegate must:

1. Enter all relevant information in the AE page of the eCRF
2. Inform the safety group and/or the Medical Monitor of the SAE via email or **fax** within 24 hours of becoming aware of the SAE.
3. Follow the initial notification with a completed SAE report form. The SAE form must be emailed or faxed to iHC within 24 hours of becoming aware of the SAE.

All SAEs that occur during the course of the study, beginning the day Informed Consent is signed, whether or not causally related to IMP must be reported immediately via fax or email (within 24 hours of the investigator becoming aware of the event) to the sponsor/designee or the Medical Monitor.

Adverse events occurring in the period between the time the subject gave written informed consent and the first exposure to IMP that meet one or more of the seriousness criteria for AEs must be reported to the sponsor/designee and the Medical Monitor in the same manner as other SAEs and will be included in the clinical study database.

Any SAE that occurs 15 days after the last dose of study drug or the last visit, whichever is later that is considered to be causally related to IMP must be **reported immediately (ie, within 24 hours of the investigator becoming aware of the event) to the sponsor/designee and the**

ZX008 (Fenfluramine Hydrochloride)
ZX008-1601 Clinical Study PA 4.0 (Japan) 25 July 2022

Medical Monitor.

Contact details and guidance for reporting SAEs will be provided to study site before the study starts.

